#### **10.1.4 The BMS-986288 █ Cohort Expansion (Part 2A)**

The primary purpose of the BMS-986288 █ Cohort Expansion (Part 2A) is to evaluate preliminary efficacy of BMS-986288. The sample size calculation will be based on the ORR.

The preliminary efficacy of BMS-986288 as a monotherapy will be evaluated in participants with advanced cutaneous melanoma and NSCLC with disease relapse/recurrence or progression after prior immunotherapy treatment with an anti-PD-1 or anti-PD-L1 containing regimen. Up to █ cutaneous melanoma participants will be treated. For NSCLC, initial evaluation of efficacy signal (ORR) will be based on approximately the first █ treated participants at a dose level. Based on the results of this initial evaluation, additional participants for a total of up to █ participants may

be treated at a dose level. If more than 1 dose level is evaluated, up to █ participants (eg, █ participants × 2 arms) may be enrolled. Other tumor types may be explored in the future.

With █ treated participants in each BMS-986288 arm, the lower limit of the 2-sided 80% Clopper Pearson CI for ORR estimate will be █ assuming ORR estimate size of █ respectively. With █ treated participants in each BMS-986288 arm, the lower limit of the 2-sided 80% Clopper Pearson CI for ORR estimate will be █ assuming ORR estimate size of █ respectively.

#### **10.1.5 The BMS-986288 in Combination with Nivolumab Cohort Expansion (Part 2B)**

The purpose of the BMS-986288 Expansion Combination Therapy (Part 2B) is to gather additional data including safety, tolerability, and preliminary efficacy for combination therapy of BMS-986288 with nivolumab in NSCLC. The sample size calculation will be based on the ORR.

Approximately █ participants will be treated. Initial evaluation of efficacy signal (ORR) will be based on approximately the first █ treated participants at a dose level and will be descriptive based on a point estimate and an 80% Clopper Pearson CI for ORR. In order for an 80% CI to exclude a █ ORR (as reported for ipilimumab with nivolumab in similar population), at least █ responders (█ ORR) will need to be observed in the first █ participants evaluated at this dose. If █ responders are observed █, the 80% CI will equal █. Based on the results of this initial evaluation, additional participants for a total of up to █ participants may be treated at a dose level. If more than 1 dose level is evaluated, up to █ participants (eg, █ participants × █ arms) may be enrolled.

In addition, if █ participants are evaluated at a dose level, there will be approximately 80% power to detect a difference between the null hypothesis assuming ORR of █ and the alternative assuming ORR of █, based on a one group  $\chi^2$  test with a 0.10 one-sided significance alpha level.

#### **10.1.6 The BMS-986288 in Combination with Nivolumab Cohort Expansion in MSS CRC Participants (Part 2C)**

Part 2C of the study uses a █ arm. A portion of the █ cohort will be █

These █ studies will have a similar design and population to Part 2C (ie, similar enrolment methods, randomized population, similar inclusion and exclusion criteria, and baseline characteristics). Approximately █ participants will be randomized in Part 2C. These █ participants will be randomized in a 2:1 ratio for the experimental arm (Arm C) and control arm (Arm D) (█ participants for the experimental arm and █ participants for the control arm). An additional dose may be open in Part 2C as Arm E (see [Section 7.2](#)). If multiple doses are open, no multiple comparison adjustments will be performed.

For each interim analysis of efficacy signal (ORR), no formal statistical comparison will be performed with a small administrative alpha of 0.0001. Interim analyses may be performed when at least █ participants in the experimental arm have at least 1 post-treatment tumor assessment

(after 49 days). This will be a descriptive evaluation based on a point estimate. The study may be stopped early if the number of responders in the treatment arm is less than the number of responders in the control arm at interim analysis. For example, using this futility criteria, Bayesian predictive probability of success (with delta ORR of [REDACTED]) is [REDACTED], with [REDACTED] responders out of [REDACTED] participants in the experimental arm and [REDACTED] responder out of [REDACTED] participants in the control arm. Based on the results of this initial evaluation, additional participants for a total of up to [REDACTED] participants may be randomized to each existing experimental arm. See [Section 10.3.8](#) for further information regarding interim analyses.

At the final analysis, there will be approximately [REDACTED] randomized participants in each experimental arm and [REDACTED] participants in the [REDACTED] arm ([REDACTED] participants from the randomized control arm and [REDACTED] participants from the [REDACTED] control data). This will provide approximately 80% power to detect the delta ORR of [REDACTED] with a two-sided alpha of 0.1. The trial can reach statistical significance when the delta ORR is [REDACTED] or larger. If it is not possible to borrow information from [REDACTED] data or studies, approximately [REDACTED] randomized participants in the experimental arm and [REDACTED] participants from the randomized control arm will be evaluated. This will provide approximately 73% power to detect the delta ORR of [REDACTED] with a two-sided alpha of 0.1 and unpooled variance assumption.

## 10.2 Populations for Analyses

For purposes of analysis, the populations are defined in Table 10.2-1.

**Table 10.2-1: Populations for Analyses**

Population	Description
Enrolled	All participants who sign informed consent and are registered into the Interactive Response Technology (IRT)
Treated	All participants who take at least 1 dose of study treatment
Response-evaluable	All treated participants with measurable disease at baseline and 1 of the following: (a) at least 1 post baseline tumor assessment; (b) clinical progression; and (c) death
Pharmacokinetic	All treated participants who have evaluable concentration-time data
Immunogenicity	All treated participants who have baseline and at least 1 post-baseline pre-infusion immunogenicity assessment
Biomarker	All treated participants with available biomarker data
Clinical outcomes population (Part 2A and Part 2B only)	All treated participants who have a valid clinical outcomes assessment at baseline and at least 1 matched on-treatment post-baseline assessment

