For Part 2C Exploratory 
 
To compare the efficacy of BMS-986288 in combination with nivolumab vs regorafenib in the 3L/4L MSS CRC setting in subgroups of [REDACTED] and mutant tumors
 
Explore the association between response with both baseline and pharmacodynamic markers in the [REDACTED]
 
To evaluate BMS-986288 PK in the MSS CRC setting in combination with nivolumab
 
To evaluate immunogenicity of BMS-986288 and nivolumab when administered as combination
 
To explore the exposure-response relationship for BMS-986288 when given as combination with nivolumab
 
	
 
ORR, DCR, DOR, PFS by BICR, and OS in the subgroups of [REDACTED] and [REDACTED] participants
 
Summary measures of change (or % change) from baseline in parameters of interest and correlation/measure of association of response and pharmacodynamic markers
 
Summary measures of PK parameters from population PK analysis
 
Summary of ADA incidence and association with PK, efficacy, hypersensitivity, and infusion-related safety events
 
Exposure-response relationship for efficacy endpoints including ORR and PFS.
 
Exposure-response relationship for safety endpoints including TRAE Grade 3+ and dose modification due to TRAE.
 

Abbreviations: 3L/4L = 3rd line/4th line; ADA = anti-drug antibody; AE = adverse event; BICR = blinded independent central review; BMS = Bristol-Myers Squibb; CRC = colorectal cancer; DCR = disease control rate; DOR = duration of response; DLT = dose-limiting toxicity; ECG = electrocardiogram; EQ-5D-5L = 5-Level EQ-5D; EQ-5D-VAS = EQ-5D Visual Analog Scale; FACIT GP5 = Functional Assessment of Chronic Illness Therapy, General Physical item; IgG = immunoglobulin G; iRECIST = modified RECIST in cancer immunotherapy trials; MSS = microsatellite

stable; MTD = maximum tolerated dose; NSCLC-SAQ = Non-small Cell Lung Cancer Symptom Assessment Questionnaire; ORR = objective response rate; OS = overall survival; OSR = overall survival rate; PFS = progression-free survival; PK = pharmacokinetics; QTc = QT interval corrected; QTcF = QT interval corrected for heart rate using Fridericia's formula; RECIST = Response Evaluation Criteria in Solid Tumors; RP2D = recommended Phase 2 dose; SAE = serious adverse event; [REDACTED] TRAE = treatment-related adverse event; [REDACTED] TTR = time to response.

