- For future infusions, the following prophylactic premedications are recommended: diphenhydramine 50 mg (or equivalent) and/or acetaminophen/paracetamol 325 to 1,000 mg should be administered at least 30 minutes before study treatment infusions. If necessary, corticosteroids (up to 25 mg of hydrocortisone or equivalent) may be used.

**Grade 3 or 4** infusion reactions require permanent discontinuation of both study treatments.

**For Grade 3 or 4 symptoms** (severe reaction, Grade 3: prolonged [ie, not rapidly responsive to symptomatic medication and/or brief interruption of infusion]; recurrence of symptoms after initial improvement; hospitalization indicated for other clinical sequelae [eg, renal impairment, pulmonary infiltrates]; Grade 4: life-threatening; pressor or ventilatory support indicated), recommendations are as follows:

- Immediately discontinue [REDACTED] study treatment. Begin an IV infusion of normal saline and treat the participant as follows: recommend bronchodilators, epinephrine 0.2 to 1 mg of a 1:1,000 solution for SC administration or 0.1 to 0.25 mg of a 1:10,000 solution injected slowly for IV administration, and/or diphenhydramine 50 mg IV with methylprednisolone 100 mg IV (or equivalent), as needed. Participant should be monitored until the Investigator is comfortable that the symptoms will not recur. Investigators should follow their institutional guidelines for the treatment of anaphylaxis. Remain at bedside and monitor participant until recovery of the symptoms.

In case of late-occurring hypersensitivity symptoms (eg, appearance of a localized or generalized pruritus within 1 week after treatment), symptomatic treatment may be given (eg, oral antihistamine or corticosteroids).

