Monotherapy in Dose Escalation (Part 1A) and BMS-986288 IV  
Cohort Expansion (Part 2A)

Study Day of Sample Collection (1 Cycle = [REDACTED])	Event	Time (Relative to Start of BMS-986288 Infusion) Hr:Min a	BMS-986288 PK Sample	BMS-986288 ADA Sample
C1D1	Predose b	00:00	X	X
	EOI	See note c	X	
		[REDACTED]	X	
C1D[REDACTED]			X	
C1D[REDACTED] (± 1 day)			X	
C1D[REDACTED] (± 2 days)			X	
C1D[REDACTED] (± 2 days)			X	
C1D[REDACTED] (± 2 days)			X	
C2D1	Predose b	00:00	X	X
	EOI	See note c	X	
C2D[REDACTED] (± 3 days)		168:00	X	
C3D1	Predose b	00:00	X	X
	EOI	See note c	X	
C4D1	Predose b	00:00	X	X
	EOI	See note c	X	
		[REDACTED]	X	
C4D[REDACTED]			X	
C5D1	Predose b	00:00	X	X
C6D1	Predose b	00:00	X	X
Every fourth cycle after C6 until EOT (C10D1, C14D1, C18D1, etc until EOT)	Predose b	00:00	X	X

**Table 9.5-2: PK and ADA Sampling Schedule for BMS-986288 IV [REDACTED]  
Monotherapy in Dose Escalation (Part 1A) and BMS-986288 IV [REDACTED]  
Cohort Expansion (Part 2A)**

Study Day of Sample Collection (1 Cycle = [REDACTED])	Event	Time (Relative to Start of BMS-986288 Infusion) Hr:Min a	BMS-986288 PK Sample	BMS-986288 ADA Sample
EOT			X	X
30-day follow-up			X	X
60-day follow-up			X	X
100-day follow-up			X	X
Grade 3+ infusion reaction			X	X

Abbreviations: ADA = anti-drug antibody; C = cycle; D = day; EOI = end of infusion; EOT = end of treatment; Hr = hour; Min = minute; [REDACTED]; PK = pharmacokinetics; [REDACTED].

- a Every effort should be taken to collect the sample as close to the designated time as possible. The actual time of collection should be recorded.
- b All predose samples should be taken within 30 minutes prior to the start of the infusion.
- c EOI PK samples should be collected when all study drug has been infused. If a flush is administered to clear the IV lines of the drug and to ensure delivery of the entire drug dose, then draw the EOI PK sample within approximately 15 minutes after end of the flush. Do not draw EOI samples from the same IV access through which the drug was administered. Refer to the Pharmacy Manual for infusion duration. If the EOI is delayed beyond the nominal infusion duration, the collection of this sample should also be delayed accordingly.
- d Sample should be collected with [REDACTED] (see [Table 9.8.3-1](#)).

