c EOI PK samples should be collected when all study drug has been infused. If a flush is administered to clear the IV lines of the drug and to ensure delivery of the entire drug dose, then draw the EOI PK sample within approximately 15 minutes after end of the flush. Do not draw EOI samples from the same IV access

through which the drug was administered. Refer to the Pharmacy Manual for infusion duration. If the EOI is delayed beyond the nominal infusion duration, the collection of this sample should also be delayed accordingly.

d Sample should be collected with [REDACTED] (see [Table 9.8.3-1](#)).

**Table 9.5-4: PK and ADA Sampling Schedule for BMS-986288 IV [REDACTED] in Combination with Nivolumab IV [REDACTED] Cohort Expansion (Part 2C Arm C, Arm E, and Arm Z)**

Study Day of Sample Collection (1 Cycle = [REDACTED])	Event	Time (Relative to Start of Nivolumab Infusion) Hr:Min a	BMS-986288 PK [REDACTED] Sample	Nivolumab PK [REDACTED] Sample	BMS-986288 ADA [REDACTED] Sample	Nivolumab ADA [REDACTED] Sample
C1D1	Predose b	0:00	X	X	X	X
	EOI	See note c	X	X		
C1D2		24:00:00	X	X		
C2D1	Predose b	0:00	X	X	X	X
	EOI	See note c	X	X		
C3D1	Predose b	0:00	X	X		
C4D1	Predose b	0:00	X	X	X	X
C6D1	Predose b	0:00	X	X	X	X
Every fourth cycle after C6 until EOT (C10D1, C14D1, C18D1, etc until EOT)	Predose b	0:00	X	X	X	X
EOT			X	X	X	X
30-day follow-up			X	X	X	X
60-day follow-up			X	X	X	X
100-day follow-up			X	X	X	X

**Table 9.5-4: PK and ADA Sampling Schedule for BMS-986288 IV [REDACTED] in Combination with Nivolumab IV [REDACTED] Cohort Expansion (Part 2C Arm C, Arm E, and Arm Z)**

Study Day of Sample Collection (1 Cycle = [REDACTED])	Event	Time (Relative to Start of Nivolumab Infusion) Hr:Min a	BMS-986288 PK [REDACTED] Sample	Nivolumab PK [REDACTED] Sample	BMS-986288 ADA [REDACTED] Sample	Nivolumab ADA [REDACTED] Sample
Grade 3+ infusion reaction			X	X	X	X

Abbreviations: ADA = anti-drug antibody; C = cycle; D = day; EOI = end of infusion; EOT = end of treatment; Hr = hour; IV = intravenous; Min = minute; PK = pharmacokinetics; [REDACTED].

a Every effort should be taken to collect the sample as close to the designated time as possible. The actual time of collection should be recorded.

b All predose samples should be taken within 30 minutes prior to the start of the first drug (eg, nivolumab) infusion.

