#### **10.3.4 Immunogenicity**

Endpoint	Statistical Analysis Methods
Incidence of anti-drug antibodies (ADAs) Baseline ADA-positive participant is defined as a participant who has an ADA-detected sample at baseline a,b ADA positive-participant is a participant with at least 1 ADA-positive sample relative to baseline after initiation of the treatment	Frequency distribution of baseline ADA-positive participants and ADA-positive participants after initiation of the treatment

a Baseline sample is the last sample before initiation of the treatment.

b Details of the immunogenicity data analysis, including ADA titers, will be provided in the Statistical Analysis Plan.

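### The Immunogenicity population requires a post-baseline pre-infusion ADA sample, which excludes every participant with a Grade 3-4 reaction at the first infusion and most others who stop before a second one

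*Combined protocol and SAP*

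**What the plan says.** Table 10.2-1 defines one immunogenicity set: "All treated participants who have baseline and at least 1 post-baseline pre-infusion immunogenicity assessment". Its parent, the treated population, is wider: "All participants who take at least 1 dose of study treatment".

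Section 10.3.4 fixes the reference sample: "Baseline sample is the last sample before initiation of the treatment". It then classifies participants without regard to when a positive sample was drawn: "ADA positive-participant is a participant with at least 1 ADA-positive sample relative to baseline after initiation of the treatment". It also tabulates participants who are ADA-positive at baseline. It names no analysis set, and it leaves further detail to the Statistical Analysis Plan.

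Tables 9.5-2, 9.5-3 and 9.5-4 mark ADA collection predose at Cycle 1 Day 1, Cycle 2 Day 1 and later cycles, at end of treatment, at the 30-, 60- and 100-day follow-up visits, and at a Grade 3 or higher infusion reaction. Predose is tied to an infusion. For monotherapy: "All predose samples should be taken within 30 minutes prior to the start of the infusion". For the combination: "All predose samples should be taken within 30 minutes prior to the start of the first drug (eg, nivolumab) infusion". The text of Section 9.5 makes the reaction-time sample permissive rather than required.

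Section 7.4.5 states that Grade 3 or 4 "infusion reactions require permanent discontinuation of both study treatments", and Table 7.4.3.1-1 agrees. In Table 4-1, one Part 2C exploratory endpoint is "Summary of ADA incidence and association with PK, efficacy, hypersensitivity, and infusion-related safety events".

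**The concern.** Entry to the analysis set depends on reaching a second infusion, which is an outcome of treatment and may itself be related to ADA. The group excluded with certainty is the one whose first infusion ended in a Grade 3-4 reaction. Those are among the events that Part 2C sets out to relate to ADA.

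Two things are at stake. ADA incidence would describe only participants who got as far as a second predose draw. The association with hypersensitivity and infusion-related events would have no first-infusion Grade 3-4 reactions in it, and the excluded participants' baseline ADA results would be lost with them. Samples taken from these participants after dosing stopped would go unused in any table built on this population.

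**Working it through.** The plan states no ADA rate, sample size or precision for immunogenicity, so there is no figure to reproduce. The main check is a trace of one participant through the rules.

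**Participant with a Grade 3-4 reaction at the first infusion**

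1. At least one dose was taken, so the participant is in the treated population (Table 10.2-1).
2. The Cycle 1 Day 1 predose sample is the last before treatment, so it is baseline and cannot count as post-baseline (Section 10.3.4).
3. The next predose ADA sample is at Cycle 2 Day 1 (Tables 9.5-2 to 9.5-4). It needs a second infusion visit, which Section 7.4.5 rules out.
4. Post-baseline ADA samples still marked are end of treatment, Day 30, Day 60 and Day 100, so 4, plus 1 at the reaction if taken. Table 2-2 lets the end-of-treatment visit be the most recent on-treatment visit, so that sample may coincide with the reaction visit. The three follow-up draws do not depend on this.
5. Post-baseline samples that precede an infusion: 0. The participant is outside the Immunogenicity population, although a positive follow-up sample would make the same participant ADA-positive under Section 10.3.4.

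Exclusion of this group follows from the rules alone and needs no assumed rate.

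**Who else is affected on the default schedule**

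Table 2-2 gives C26D1 as an example of the last visit after all scheduled cycles, and treatment lasts up to 2 years: about 730 / 26 = 28 days per cycle. Cycle 2 Day 1 is then about Day 29. Section 10.1.6 counts the first post-treatment tumor assessment after 49 days. Since 29 < 49, a participant dosed on schedule who progresses at the first scheduled scan has already passed the Cycle 2 Day 1 draw and qualifies. Those affected are participants who stop for any reason before about Day 29.

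**Illustrative effect on incidence (assumed inputs)**

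Let d be the share excluded, p_r the ADA rate in those retained and p_d the rate in those excluded. Incidence over everyone with a post-baseline sample is (1 - d) x p_r + d x p_d. Reported incidence is p_r. The difference, reported minus full, is d x (p_r - p_d). With p_r = 10%:

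| d | p_d = 10% | p_d = 30% | p_d = 50% |
|---|---|---|---|
| 2% | 10.0% | 10.4% | 10.8% |
| 5% | 10.0% | 11.0% | 12.0% |
| 10% | 10.0% | 12.0% | 14.0% |
| 15% | 10.0% | 13.0% | 16.0% |

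Reported incidence is 10.0% in every cell, so the difference runs from 0 to -6.0 points.

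The documents offer one rough anchor for reactions alone. Section 5.5.1 reports ipilimumab infusion-related reactions in 2.2% and 4.3% of patients, with no grade given. Suppose, as an extreme, that 4.3% all had Grade 3-4 reactions at the first infusion and p_d were 50%. The difference would be 0.043 x (10 - 50) = -1.7 points. At 2.2% it would be 0.022 x (10 - 50) = -0.9 points.

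**Illustrative effect on the association**

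Take 8 Grade 3-4 infusion reactors (assumed). If 25%, 50%, 75% or 100% of them react at the first infusion, then 8 x (1 - share) = 6, 4, 2 or 0 can remain in the set. The number of first-infusion reactors among them is 0 in every case.

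**The case against.** The strongest reply is that the literal exclusion is real but narrow, and much of it stands.

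- **Early progressors.** A reader might infer that they drop out of the ADA-efficacy association. The day counts above do not support that on the default schedule. Only death, clinical deterioration, unscheduled progression or another exit before the second infusion matters.
- **All one-dose participants.** A reader might infer that every one of them is excluded. Section 9.5 foresees a predose sample drawn before a dose that is then delayed. If a Cycle 2 Day 1 sample is drawn and the dose is then withheld for good, the text does not say whether it counts as pre-infusion. This cannot help first-infusion Grade 3-4 reactors, who have already been discontinued.
- **Time order.** ADA first detected at the 30-, 60- or 100-day visit arose or was found after a first-infusion reaction and cannot explain it. Baseline ADA could, and so could a reaction-time sample, but Section 9.5 only permits that one. This limits what restoring the participants can show, and the fix has to allow for it.
- **Analysis set.** Section 10.3.4 names none, and a rule for calling a participant positive is not a rule for entering a population. The two texts are mismatched rather than in direct contradiction. That the ADA analyses use the Table 10.2-1 set is an inference, though no other ADA population is defined. The Statistical Analysis Plan could still change it.
- **Alternative dosing.** In Appendix 8 Table 5 the Cycle 2 Day 1 ADA sample precedes no infusion, so entry waits for Cycle 3 Day 1. That schedule is monotherapy only and may never be used; in the combination table (Table 6), Cycle 2 Day 1 is predose. It adds little.
- **Importance.** ADA is exploratory in every part, and Section 5.5.4.5 describes infusion reactions, including high-grade hypersensitivity, as uncommon with nivolumab or BMS-986288.

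One possible defence of the restriction, interference from circulating drug, is not stated in the documents. It would not obviously justify dropping the 60- and 100-day samples, which are drawn well after dosing has stopped.

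**Conclusion.** The point holds in a limited form. On the stated rules, every participant with a Grade 3-4 reaction at the first infusion is outside the only defined immunogenicity population. So are most others who stop before a second infusion, with the withheld Cycle 2 Day 1 dose left open. Provided that population is used for the ADA analyses, incidence omits these participants, and the Part 2C association, including that with baseline ADA, has no first-infusion Grade 3-4 events.

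A reader might infer that reported ADA incidence is materially too low. The documents do not support that. They give neither an ADA rate nor an early-stopping rate, the difference is zero if the excluded and retained groups have the same rate, and the excluded group is probably small. The figures above show how the difference behaves under assumed inputs; they do not estimate it. The loss of first-infusion Grade 3-4 reactors from the association needs no such assumption. Because the endpoints are exploratory, this is an inexpensive improvement to make before the analysis plan is finalized. It does not threaten any primary or secondary conclusion.

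**What to change.** In Table 10.2-1 and the Statistical Analysis Plan, define the Immunogenicity population as treated participants with a baseline ADA result and one or more post-baseline ADA results, whatever their timing relative to an infusion. This fits the positivity rule in Section 10.3.4 and the sampling in Tables 9.5-2 to 9.5-4. It also settles the case of a Cycle 2 Day 1 sample followed by a withheld dose.

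Name this population in Section 10.3.4 and for the Part 2C association endpoint. Keep the pre-infusion-only set as a sensitivity analysis. In the infusion-reaction association, report ADA present at or before the reaction (baseline or reaction-time sample) separately from ADA first detected afterwards.

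The cost is a wording change and one additional tabulation. No samples or visits are added, and the discontinuation rules are untouched. The small downside is that some added participants will contribute only one or a few post-baseline samples, some possibly taken while drug is still present. The sensitivity analysis shows whether that matters.
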